The safety monitoring plan will require weekly liver function tests (LFTs) including AST, ALT alkaline phosphatase, gamma-glutamyl transpeptidase (GGT), and total bilirubin during treatment with urelumab ([Table 5.1-1](#)), and weekly for the first 8 weeks following last treatment with urelumab ([Table 5.1-3](#)). As detailed in [Section 5.3.1](#) and Hepatotoxicity management algorithm ([Appendix 3](#)):

Management of LFT Elevations:

- Subjects experiencing \geq Grade 3 elevations in ALT, AST, or total bilirubin will be discontinued.
- Subjects experiencing ALT or AST $>$ 3x ULN with concurrent total bilirubin $>$ 2x ULN and fulfilling Hy's law criteria will be discontinued. If 2 events of Hy's Law (ALT or AST $>$ 3 X ULN and concurrent T Bili $>$ 2 X ULN) occurs at any

point in the study the entire cohort and all cohorts above will be considered to exceed the MTD and no subject will receive further doses at or above that dose level.

- Subjects experiencing Grade 2 elevations in ALT, AST or total bilirubin will have the next planned dose delayed until ALT, AST, and total bilirubin resolve to \leq Grade 1

2) **Hepatotoxicity management algorithm:** To mitigate risk to subjects who develop drug-related hepatotoxicity, specific guidelines and algorithm for management of hepatotoxicity (see [Appendix 3](#)), with links to online resources with a comprehensive listing of potentially hepatotoxic agents are included in this protocol.

Screening tests, and clinical and laboratory safety assessments will also be performed on an ongoing basis and monitored closely. In addition, the AEs and SAEs will be reviewed by the Medical Monitor/Study Director and the Pharmacovigilance group to look for trends and safety issues. It is possible that unforeseen, unknown, or unanticipated reactions may occur since urelumab is an investigational product.

In addition to the potential risk associated with administration of study drugs, there is also some risk associated with tumor biopsies, including bleeding, infection and pain. While there is no direct benefit to subjects who undergo these procedures, there is the distinct possibility that the data generated from these samples will guide the further development of these compounds and may be of direct benefit for others with advanced solid tumors.

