- d) The first 20 subjects with MEL and SCCHN in the Stage 1 of the expansion will be required to undergo mandatory pre-treatment and on-treatment biopsies in the cohort expansion phase at acceptable clinical risk as judged by the investigator. Biopsies in the MEL and SCCHN cohorts must be excisional, incisional, or core needle biopsies. The biopsy lesion must be distinct from a target lesion.
- e) All subjects in the DLBCL and FL expansion cohorts will be required to undergo mandatory pre-treatment biopsies and the first 20 subjects in Stage 1 of the expansion phase will be required to undergo mandatory on-treatment biopsies with adequate tissue collection to perform specified analyses. The biopsy lesion must be distinct from an index lesion. Note: The only exception permissible is in sole accessible, bulky lesions that are > 5 cm in largest diameter. Lesions meeting this criterion can be biopsied and followed as an index lesion.
- f) ECOG status of 0 or 1.
- g) Adequate organ function for subjects with solid tumor histologies as defined by the following (institutional levels of lab normal values based on ethnicity will be allowed for WBC, ANC, and Hemoglobin):
 - i) WBC \geq 2000/ μ L (stable off any growth factor within 4 weeks of first study drug administration)
 - ii) Neutrophils \geq 1500/ μ L (stable off any growth factor within 4 weeks of first study drug administration)

- iii) Platelets $\geq 100 \times 10^3/\mu\text{L}$ (transfusion to achieve this level is not permitted within 2 weeks of first study drug administration)
- iv) Hemoglobin $\geq 8.5 \text{ g/dL}$ (transfusion to achieve this level is not permitted within 2 weeks of first study drug administration)
- v) Creatinine $\leq 1.5 \times \text{ULN}$
- vi) ALT and AST $\leq 3 \times \text{ULN}$
- vii) Total bilirubin $\leq 1.5 \times \text{ULN}$ (except subjects with Gilbert's Syndrome who must have normal direct bilirubin)
- viii) Normal thyroid function, subclinical hypothyroidism (TSH $< 10 \text{ mIU/mL}$) or have controlled thyroid disorder

h) Adequate organ function for subjects with B-cell NHL malignancies as defined by the following:

- i) Absolute Neutrophil Count $\geq 750/\mu\text{L}$ (no WBC growth factors for prior 14 days)
- ii) Platelets $\geq 50 \times 10^3/\mu\text{L}$ (no platelet transfusions for prior 14 days)
- iii) Hemoglobin $> 8.0 \text{ g/dL}$ (no RBC transfusions for prior 7 days)

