4.5.2 Dose Limiting Toxicities

Adverse events will be graded according to the National Cancer Institute (NCI) Common Terminology Criteria for Adverse Events (CTCAE) Version 4.0 (v4.0).

Non-hematologic Dose-Limiting Toxicity (DLT):

A. Hepatic Non-Hematologic DLT

Any one of the following study drug-related events will be considered a hepatic DLT:

- Any \geq grade 3 elevation of AST, ALT or T bili
- Grade 2 AST or ALT with symptomatic liver inflammation (eg, right upper quadrant tenderness, jaundice, pruritus)
- AST or ALT $> 3 \times$ ULN and concurrent total bilirubin $> 2 \times$ ULN without initial findings of cholestasis (elevated serum alkaline phosphatase (ALP) (ie, findings consistent with Hy's law or FDA definition of potential drug-induced liver injury or pDILI)*

*[Note that this special category of DLT uses ULN rather than CTC Grade for definition]

NOTE: Subjects who experience a DLT that is considered related only to urelumab may be allowed to continue nivolumab monotherapy following resolution of the event. This will be determined on a case by case basis, after specific consultation and agreement between the investigator and BMS Medical Monitor in settings where benefit/risk may justify continued treatment with nivolumab

monotherapy (eg, subjects with asymptomatic, isolated grade 3 ALT and/or AST elevation that responds rapidly to short 2-3 weeks course of steroid therapy).

B. Non-Hepatic Non-Hematologic DLT

Any of the following events will be considered a Non-Hepatic Non-Hematologic DLT:

- Any Grade 2 drug-related uveitis or eye pain or blurred vision that does not respond to topical therapy and does not improve to Grade 1 severity within 2 weeks OR requires systemic treatment
- Grade 3 drug-related uveitis, pneumonitis, bronchospasm, neurologic toxicity, hypersensitivity reaction, or infusion reaction of any duration requires discontinuation
- Any Grade 3 or greater non-dermatologic, non-hepatic non-hematologic study drug-related toxicity will be considered a dose-limiting toxicity with the following specific EXCEPTIONS:
 - Grade 3 or grade 4 electrolyte abnormalities that are not complicated by associated clinical adverse experiences, last less than 48 hours and either resolve spontaneously or respond to conventional medical intervention
 - Grade 3 nausea, vomiting or diarrhea that lasts less than 48 hours, and either resolves spontaneously or responds to conventional medical intervention

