4.5.6 Criteria to Resume Treatment

Subjects experiencing AEs not meeting criteria for permanent discontinuation as outlined in [Section 4.5.7](#) may resume treatment with study medication under the following criteria:

- Subjects may resume treatment with study drug when the drug-related AE(s) resolve to Grade ≤ 1 or baseline value with the following exceptions:
 - Subjects may resume treatment in the presence of Grade 2 fatigue;
 - Subjects who have not experienced a Grade 3 drug-related skin AE may resume treatment in the presence of Grade 2 skin toxicity;
 - Subjects with Grade 2 uveitis or eye pain or blurred vision not meeting DLT criteria ([Section 4.5.2](#)) must resolve to baseline prior to resuming study therapy;
 - Drug-related pulmonary toxicity, diarrhea, or colitis, must have resolved to baseline before treatment is resumed;
 - Drug-related endocrinopathies adequately controlled with only physiologic hormone replacement may resume treatment.

NOTE: Subjects who experience a DLT that is considered related only to urelumab may be allowed to continue nivolumab monotherapy following resolution of the event. This will be determined on a case by case basis, after specific consultation and agreement between the investigator and BMS Medical Monitor in settings where benefit/risk may justify continued treatment with nivolumab monotherapy (eg, subjects with asymptomatic, isolated grade 3 ALT and/or AST elevation that responds rapidly to short 2-3 weeks course of steroid therapy).

If the criteria to resume treatment are met, the subject should restart treatment at the next scheduled time point per protocol.

The consideration to re-initiate study therapy under these exceptions will be made on a case by case basis after considering the overall benefit/risk profile and in consultation between the investigator and the study sponsor. Any adverse event with clinical risk will be assessed on a case by case basis with the investigator and the BMS Medical Monitor to determine the risks and benefits of continuing on therapy following resolution versus discontinuing therapy permanently.

If treatment with study medication is delayed > 6 weeks, the subject must be permanently discontinued from study therapy, except as specified in [Section 4.5.7](#)).

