4.5.7 Guidelines for Permanent Discontinuation

Subjects will be required to permanently discontinue both study drugs for the following adverse events:

- A. Any drug related AE occurring at any time that meets DLT criteria as outlined in [Section 4.5.2](#) will require permanent discontinuation with the following **exceptions**:
 - a) grade 3 diarrhea, nausea, vomiting, or abdominal pain that returns to grade 1 or baseline within 3 days with medical intervention;
 - b) grade 3 pruritus or rash that returns to grade 1 or baseline within 7 days or baseline with medical intervention;
 - c) grade 4 electrolyte abnormalities that < 72 hours in duration;
 - d) grade 4 neutropenia \leq 7 days in duration;
 - e) grade 4 increase in amylase or lipase that is not associated with clinical or radiographic evidence of pancreatitis;
 - f) grade 4 lymphopenia < 5 days in duration.

NOTE: Subjects who experience a DLT that is considered related only to urelumab may be allowed to continue nivolumab monotherapy following resolution of the event. This will be determined on a case by case basis, after specific consultation and agreement between the investigator and BMS Medical Monitor in settings where benefit/risk may justify continued treatment with nivolumab monotherapy (eg, subjects with asymptomatic, isolated grade 3 ALT and/or AST elevation that responds rapidly to short 2-3 weeks course of steroid therapy).

Any dosing delay lasting > 6 weeks will be cause for permanent discontinuation with the following exceptions:

- Dosing delays to allow for prolonged steroid tapers to manage drug-related adverse events are allowed. Prior to re-initiating treatment in a subject with a dosing delay lasting > 6 weeks, the BMS Medical Monitor must be consulted. Tumor assessments should continue as per protocol even if dosing is delayed.

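### For drug-related Grade 2 AST/ALT elevation with symptomatic liver inflammation, Protocol Section 1.5 states only a dose delay, while Sections 4.5.2 and 4.5.7 require permanent discontinuation; the resumption criterion also differs between Sections 1.5 and 4.5.6

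*Protocol*

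**What the plan says.** Protocol Section 1.5, in its list on managing liver function test (LFT) elevations, sets out actions by grade:

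- For Grade 3 or higher, subjects with "elevations in ALT, AST, or total bilirubin will be discontinued". A separate bullet discontinues Hy's law cases.
- For Grade 2, "Subjects experiencing Grade 2 elevations in ALT, AST or total bilirubin will have the next planned dose delayed until" all three values have come down to Grade 1 or lower. The bullet does not distinguish symptomatic from asymptomatic elevations, or drug-related from unrelated ones.

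Protocol Section 4.5.2 A opens with "Any one of the following study drug-related events will be considered a hepatic DLT" and includes in its list "Grade 2 AST or ALT with symptomatic liver inflammation (eg, right upper quadrant tenderness, jaundice, pruritus".

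Protocol Section 4.5.7 states: "Subjects will be required to permanently discontinue both study drugs for the following adverse events". Item A is "Any drug related AE occurring at any time that meets DLT criteria as outlined in" Section 4.5.2, subject to exceptions a) to f). A NOTE, repeated in Sections 4.5.2 and 4.5.6, lets a subject whose DLT is attributed only to urelumab go on with nivolumab alone, by case-by-case agreement with the Medical Monitor.

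Protocol Section 4.5.6 lets subjects whose events do not meet Section 4.5.7 resume when drug-related events resolve to Grade 1 or lower "or baseline value with the following exceptions".

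**The concern.** Hepatotoxicity is the main risk that the protocol names for urelumab, and the list in Section 1.5 is presented as part of the plan to limit it. For one type of liver event, that list and the dosing sections do not give the same instruction. A site working from Section 1.5 would see a delay with a laboratory condition for the next dose; a site working from Sections 4.5.2 and 4.5.7 would see the end of combination treatment.

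What is at stake is first the subject's further exposure to urelumab, and second consistency across sites. SAP Section 7.6.3 identifies events leading to discontinuation by the recorded action taken, so identical events managed under different passages could fall inside that table at one site and outside it at another.

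**Working it through.** No arithmetic applies, and the plan states no figure on this point. The check applies each passage to one test case: a study drug-related Grade 2 ALT or AST elevation with symptomatic liver inflammation, below Grade 3 and not meeting Hy's law.

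| Step | Protocol place | Result for the test case |
|---|---|---|
| 1 | 1.5, Grade 3 and Hy's law bullets | Do not apply |
| 2 | 1.5, Grade 2 bullet | Next dose delayed until ALT, AST and total bilirubin are Grade 1 or lower; nothing further stated |
| 3 | 4.5.2 A | Hepatic DLT |
| 4 | 4.5.7 A | Permanent discontinuation of both drugs, whenever the event occurs |
| 5 | 4.5.7 exceptions a) to f) | Cover gastrointestinal events, pruritus/rash, electrolytes, neutropenia, amylase/lipase and lymphopenia; none is hepatic |
| 6 | NOTE in 4.5.2, 4.5.6 and 4.5.7 | At most nivolumab alone, case by case, if attributed only to urelumab |
| 7 | 4.5.6 | Resumption criteria not available, because the event meets 4.5.7 |

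Steps 2 and 4 differ, and steps 5 to 7 do not close the gap: no route in Sections 4.5.2 to 4.5.7 returns this subject to the combination.

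Changing the test case shows where the conflict ends. If the elevation is asymptomatic, or not drug-related, the symptomatic Grade 2 criterion in Section 4.5.2 A is not met, Section 4.5.7 A is not triggered by it, and this conflict does not arise.

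For a drug-related Grade 2 event that does not meet Section 4.5.7, a second difference remains. Section 1.5 requires Grade 1 or lower for all three values. Section 4.5.6 accepts either Grade 1 or lower or the baseline value. The two criteria coincide unless a subject's baseline lies above Grade 1.

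The last check is whether another passage settles precedence.

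- Section 1.5 says that its list is detailed in Section 5.3.1 and Appendix 3. Section 5.3.1 describes LFT monitoring and itself points to Appendix 3 for management.
- Section 4.5.5 also sends Grade 2 hepatic events to the Appendix 3 algorithms. Appendix 3 is not in the protocol text available here, so its handling of symptomatic Grade 2 events could not be checked.
- The Synopsis says that DLT-defining events lead to interruption, permanent discontinuation or both, and refers to Sections 4.5.5 and 4.5.7. It does not mention Section 1.5.

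**The case against.** The strongest reply is that Section 1.5 is a risk/benefit summary and that the operative text already decides the matter. The Synopsis, Section 3.1.2 and Section 3.5 all refer to Section 4.5.7 for stopping treatment, and none sends a site to Section 1.5 for dosing. Sections 4.5.5 and 4.5.6 open resumption only to subjects who do not meet the permanent discontinuation rules. The Section 1.5 bullet can also be read as a minimum laboratory condition, with the DLT rule applying on top of it.

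Much of this stands, and it lowers the practical risk: a site that follows Sections 4.5.5 to 4.5.7 would not be misled. It does not remove the conflict. Section 1.5 is written as instruction, not background. It contains an operative rule that appears nowhere else in the available text, namely that two Hy's law events put the cohort and all higher cohorts over the MTD. Its Grade 2 bullet refers to neither Section 4.5.2 nor Section 4.5.7.

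A reader might infer more than the documents support:

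- **That Section 1.5 entitles the subject to be re-dosed.** The bullet says how long to delay. It does not say that laboratory recovery alone is sufficient, or that other stopping rules lapse.
- **That DLT counts, the MTD or escalation decisions are affected.** DLT status comes only from Section 4.5.2, and the Grade 2 bullet reclassifies nothing. The event enters the escalation table in the same way whichever passage guides later dosing.
- **That subjects with Gilbert's syndrome would be lost.** Section 3.3.1 admits them above the usual bilirubin limit ("except subjects with Gilbert's Syndrome who must have normal direct bilirubin" for solid tumors), so the baseline alternative might seem decisive for them. That needs bilirubin grade cut-offs, which the documents do not give. Sections 4.5.5 and 4.5.7 also allow the Medical Monitor to agree delays beyond 6 weeks, so loss would not be automatic.

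**Conclusion.** The point holds as a narrow internal contradiction. For study drug-related Grade 2 AST/ALT with symptomatic liver inflammation, Section 1.5 states only a delay, while Sections 4.5.2 A and 4.5.7 A end combination treatment. Separately, Sections 1.5 and 4.5.6 give different resumption criteria for Grade 2 liver events that do not require discontinuation.

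The number of subjects affected cannot be estimated. The only on-study liver rates given are Grade 3/4 ALT/AST elevations (2%/2% of 138 patients, preliminary data in Section 1.5). There is no Grade 2 rate and no proportion with symptoms.

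The conclusion assumes that Appendix 3 does not already resolve the difference. It takes no position on which rule is clinically right.

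**What to change.** Reconcile the Grade 2 bullet in Section 1.5 with Sections 4.5.2 A, 4.5.6 and 4.5.7 A, and check the result against Appendix 3. One rule should then apply to drug-related symptomatic Grade 2 AST/ALT elevation, and one resumption criterion, with or without the baseline alternative, to Grade 2 liver events that do not require discontinuation. Replace the bullet in Section 1.5 with a cross-reference to the reconciled text. The choice of rule and criterion belongs to the sponsor's clinical team.

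The cost is protocol wording only: no new procedures, subjects or analyses.

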2 ETHICAL CONSIDERATIONS

2.1 Good Clinical Practice

This study will be conducted in accordance with Good Clinical Practice (GCP), as defined by the International Conference on Harmonisation (ICH) and in accordance with the ethical principles underlying European Union Directive 2001/20/EC and the United States Code of Federal Regulations, Title 21, Part 50 (21CFR50).

The study will be conducted in compliance with the protocol. The protocol and any amendments and the subject informed consent will receive Institutional Review Board/Independent Ethics Committee (IRB/IEC) approval/favorable opinion prior to initiation of the study.

All potential serious breaches must be reported to BMS immediately. A serious breach is a breach of the conditions and principles of GCP in connection with the study or the protocol, which is likely to affect, to a significant degree, the safety or physical or mental integrity of the subjects of the study or the scientific value of the study.

Personnel involved in conducting this study will be qualified by education, training, and experience to perform their respective tasks.

This study will not use the services of study personnel where sanctions have been invoked or where there has been scientific misconduct or fraud (eg, loss of medical licensure, debarment).

2.2 Institutional Review Board/Independent Ethics Committee

Before study initiation, the investigator must have written and dated approval/favorable opinion from the IRB/IEC for the protocol, consent form, subject recruitment materials (eg, advertisements), and any other written information to be provided to subjects. The investigator or BMS should also provide the IRB/IEC with a copy of the Investigator Brochure or product labeling information to be provided to subjects and any updates.

The investigator or BMS should provide the IRB/IEC with reports, updates and other information (eg, expedited safety reports, amendments, and administrative letters) according to regulatory requirements or institution procedures.

2.3 Informed Consent

Investigators must ensure that subjects are clearly and fully informed about the purpose, potential risks, and other critical issues regarding clinical studies in which they volunteer to participate.

In situations where consent cannot be given to subjects, their legally acceptable representatives (as per country guidelines) are clearly and fully informed about the purpose, potential risks, and other critical issues regarding clinical studies in which the subject volunteers to participate.

BMS will provide the investigator with an appropriate (ie, Global or Local) sample informed consent form(s) which will include all elements required by ICH, GCP and applicable regulatory requirements. The sample informed consent form will adhere to the ethical principles that have their origin in the Declaration of Helsinki.

Investigators must:

- Provide a copy of the consent form(s) and written information about the study in the language in which the subject is most proficient prior to clinical study participation. The language must be non-technical and easily understood.
- Allow time necessary for subject or subject's legally acceptable representative to inquire about the details of the study.
- Obtain an informed consent signed and personally dated by the subject or the subject's legally acceptable representative and by the person who conducted the informed consent discussion.

- Obtain the IRB/IEC's written approval/favorable opinion of the written informed consent form(s) and any other information to be provided to the subjects, prior to the beginning of the study, and after any revisions are completed for new information.
- If informed consent is initially given by a subject's legally acceptable representative or legal guardian, and the subject subsequently becomes capable of making and communicating his or her informed consent during the study, consent must additionally be obtained from the subject.
- Revise the informed consent whenever important new information becomes available that is relevant to the subject's consent. The investigator, or a person designated by the investigator, should fully inform the subject or the subject's legally acceptable representative or legal guardian, of all pertinent aspects of the study and of any new information relevant to the subject's willingness to continue participation in the study. This communication should be documented.

The confidentiality of records that could identify subjects must be protected, respecting the privacy and confidentiality rules applicable to regulatory requirements, the subjects' signed ICF and, in the US, the subjects' signed HIPAA Authorization.

The consent form(s) must also include a statement that BMS and regulatory authorities have direct access to subject records.

The rights, safety, and well-being of the study subjects are the most important considerations and should prevail over interests of science and society.

